6.4.4 Every 6 months after enrollment

- TIP-RFT
- MOS-SSS
- ASCQ-Me QOC
- PedsQL-SCD Module

6.4.5 Every 12 months after enrollment

• Health Care Transition Feedback Survey for Youth/Young Adults

6.4.6 End of Study

- Demographic update: any change in participant's demographics (e.g. zip code of residence, presence of a sibling, parent or child with SCD, academic achievement, disability status, marital status, employment status, living arrangement, and household income)
- Healthcare Utilization Data Collection: acute care utilization history (ED/ urgent care visits and hospital admissions) and ambulatory care visits (SCD provider and primary care provider) in the preceding 3 months
- TIP-RFT
- MOS-SSS
- ASCO-Me OOC
- PedsOL-SCD Module
- Health Care Transition Feedback Survey for Youth/Young Adults

6.5 Schedule of Assessments (Mentors/Advisors)

6.5.1 Screening

Subjects who consent for participation and meet the eligibility criteria for enrollment into this study as mentors or advisors will undergo the following screening assessments (See Section 3.4 for additional details on assessments):

- Date of birth
- Race
- Ethnicity
- Gender
- Sickle cell genotype
- Zip code of residence (to determine urban or rural residency status)
- Presence of a sibling, parent, or child (first degree relative) with SCD
- Academic achievement
- Disability status
- Marital status
- Employment status
- Living arrangement
- Household income
- Age at transfer to adult care
- Type of SCD adult provider (primary care versus specialty)
- Mentor matching (Peer Mentoring sites only)
- Advisor matching (Peer Mentoring sites only)

6.5.2 Study Completion

• Demographic update: any change in participant's demographics (e.g. zip code of residence, presence of a sibling, parent, or child with SCD, academic achievement, disability status, marital status, employment status, living arrangement, and household income).

6.6 Schedule of Assessments – Quality Improvement (All Clinical Sites)

6.6.1 Baseline QI Assessment

- Health Care Transition Process Measurement Tools:
 - o For Transitioning Youth to Adult Healthcare Providers (pediatric clinics)
 - o For Integrating Young Adults to Adult Healthcare Providers (adult clinics)
- Provider Satisfaction with Transition Programming Feedback survey

6.6.2 Monthly QI Activities After Baseline Assessment

- Site Transition Team will meet monthly to work on implementing the Six Core Elements of transition
- Sites will attend monthly coaching calls hosted by the study QI team

Sites will be directed to submit their progress on QI initiatives (specifically
monthly chart audits on the number of completed readiness basement and
emergency care plans) once they have completed the training on QI data
collection

• Sites will participate in ongoing Community Advisory Board meetings with local Community-Based Organization per CBO required calendar.

6.6.3 Every 6 months QI Assessment

- Health Care Transition Process Measurement Tools
 - o For Transitioning Youth to Adult Healthcare Providers (pediatric clinics)
 - o For Integrating Young Adults to Adult Healthcare Providers (adult clinics)
- A formal ST3P-UP study site visit by the coordinating center's QI team will be done with each site to review progress and support QI initiatives in addition to reviewing overall study progress as the site. This may be either in person or virtually.

6.6.4 Every 12 months QI Assessment

 Provider Satisfaction with Transition Programming Feedback survey is administered annually

7. REMOVAL OF SUBJECTS FROM STUDY

7.1 Off Study

Subjects may stop their participation in this study at any time if they no longer wish to participate, or if the investigator believes this to be in the best interest of the subject. When subjects are removed from the study, the reason for study removal and date the subject was removed should be documented in the ST3P UP REDCap database. Reasons a subject may be removed from study include, but are not limited to:

- Subject non-compliance with study participation, in the opinion of the investigator
- The subject or legal representative (such as a parent or legal guardian) withdraws study consent
- The subject is lost to follow-up
- Study completion
- Investigator's decision to withdraw the subject
- Subject death

Subjects who have been lost to follow-up for a period without three documented follow up attempts, should be transitioned off study due to lack of compliance with the study required visits per protocol. The off-study date should be documented in the EDC as the day the PI deems the subject as coming off study. This date must correlate with the end of available utilization data after every effort has been made to collect and enter available utilization and survey data. In the event of discrepancy between the documented consecutive attempts to reach the patient and utilization data, please review the data with the DCC PIs to ensure the most appropriate date for

lost to follow up is documented. HIPAA guidelines must be followed. A copy of all communication sent to the subject will be maintained in the research chart.

Subjects that are off study will not participate in future or additional study-related procedures, including data collection.

Subjects who remain enrolled at the completion of the funded project will be off study on the date of study completion.

Subjects that are consented (but not enrolled on study) and withdraw participation will not be required to complete the end of study CRF. Documentation of study withdrawal should be maintained in the research chart.

7.2 Special Considerations

- Pregnancy: If pregnancy should occur post enrollment, the site PI should consult with the Sponsor to determine if the subject should continue to participate in the study.
- Subject Relocation: If subjects relocate away from a study site, the site PI should consult with the sponsor to determine the impact this will have on the subject's continued study participation.
- Other Forms of Mentoring: As part of this project, clinical sites cannot implement concurrent 1:1 mentoring program for patients in their practice regardless of site randomization status. Partner CBOs also cannot implement 1:1 mentoring for their clients with SCD. Many sites offer group mentoring activities such as support groups, girl/guy talks, etc. This is acceptable regardless of sites' randomization status.
- The use of Community Health Workers (CHW) is also common practice among CBO partners and is commonly used in clinical care. Therefore, with the exclusion on 1:1 mentoring, CHW can serve as a source of support for SCD clients regardless of randomization status.

8. DATA AND SAFETY

8.1 Safety Monitoring

This protocol will be monitored according to the processes in effect for all LCI investigator-initiated studies and the protocol-specific monitoring plan and will abide by standard operating procedures (SOPs) set forth by both Atrium Health (formerly known as Carolinas Healthcare System) Office of Clinical and Translational Research and LCI (and/or other participating institutional SOPs). It is the responsibility of the Sponsor-Investigator to monitor any safety data (i.e., unanticipated problems/potential risks, as per Section 9, regularly to monitor subject consents, enrollment and retention, safety data, and validity/integrity of the data. Documentation of these meetings will be kept with the study records. The LCI Data and Safety Monitoring Committee will provide central monitoring oversight for this study. This will be performed under the auspices of the LCI Data Safety Monitoring Plan. The Sponsor-Investigator will submit data to the LCI Data and Safety Monitoring Committee as required.

8.2 Data Monitoring

This study will be organized, performed, and reported in compliance with the study protocol, SOPs of the LCI and Atrium Health (formerly known as Carolinas Healthcare System) Offices of Clinical and Translational Research (and/or other participating institutional SOPs), and other applicable regulations and guidelines (e.g. ICH GCP).

Subjects will be monitored by each participating institution, as per their guidelines and policies. The LCI Research QA Department and the DCC will maintain central oversight. Data from this study will be collected on paper and/or electronic case report forms (eCRFs) and from study-specific applications. Monitoring will be done by comparing source documentation to the eCRFs. Any variation between the two data sets will be discussed with the Investigator and/or other study team members as appropriate. Investigators and their relevant personnel must be available during the monitoring visits and must allocate enough time to be devoted to the monitoring process.

Levine Cancer Institute (of Atrium Health, formerly known as Carolinas Healthcare System) will be the central data coordination and monitoring center for this study and will provide monthly progress reports to the Scientific Oversight Group. This will include monitoring of enrollment, derivation of study endpoints, data logic checks, assessment of data missingness, attrition, and safety. Importantly, ongoing estimation and monitoring of the coefficient of variation of site enrollment size will be conducted. This will allow risk-mitigating adjustments to the study enrollment strategy in the event it becomes apparent that the cluster size coefficient of variation markedly deviates from initial assumptions. Similarly, ongoing estimates and monitoring of the intra-class correlation [ICC] for acute care utilizations will be conducted. The cadence of the central monitoring will be monthly. Comprehensive monitoring reports will be provided to the Sponsor-Investigator, while reports focusing on enrollment, subject disposition, and safety will be provided to the Scientific Oversight Group. The goals of the data coordination and monitoring function include assurance of subject safety, and risk mitigation regarding enrollment targets, key design assumptions, and data quality.

9. POTENTIAL RISKS/UNANTICIPATED PROBLEMS

9.1 Potential Risks

In general, involving clinical practices in QI processes to standardize care delivery is widespread and accepted as posing no additional risk to the patient.

9.1.1 Subject Confidentiality

All data and records generated during this study will be kept confidential in accordance with Institutional policies on subject privacy and HIPAA; the investigators and other site personnel will not use such data and records for any purpose other than conducting the study. No breach of confidentiality is anticipated as no records will be shared with any personnel outside the research team. All medical information including assessments and other medical records will be recorded and stored in a database. The database will exist on password protected secured servers. All records will be kept confidential.

Calls between mentors and mentees will be recorded and may be monitored for safety purposes. Contacts between advisors and mentors via SMS messaging will be saved and may be monitored for safety purposes.

To minimize risks to confidentiality, data will only be monitored by the Principal Investigators and trained research staff. At a minimum, research staff will have completed basic human subject protection research training that includes content on vulnerable subjects (children).

Study platform vendor (InquisitHealthTM) will utilize a 3rd party vendor (CheckrTM) to conduct background checks for mentors and advisors and will make every effort to ensure confidentiality and protection of participants' information. Mentors and advisors will be asked to complete a W9 to facilitate participant reimbursement (if applicable). SickleSoft, Inc LLC, the ST3P UP Application developer, will provide oversight and manage access for sites roles within the application. They will make every effort to ensure confidentiality and protection of participants' information.

9.1.2 Emotional Distress

Some study activities can make participants feel uncomfortable, anxious, and/or emotionally fatigued which are symptoms of emotional distress. If an EA-SCD, mentor, or advisor experiences and reports emotional distress, study activities will be paused until the issue is resolved (see reporting in Section 9.2.2).

9.2 Unanticipated Problems (UAP)

9.2.1 Definition

A UAP is any incidence, experience or outcome that is unexpected (e.g., a lost or stolen laptop computer that contains sensitive study information) given the information provided in research- related documentation (e.g., informed consent) and the study population characteristics, that is related or possibly related to participation in the research study and places the participant at an increased risk.

9.2.2 Reporting

All EA-SCD UAPs related to study activities will be reported to the site study team by the participant. It is the responsibility of the site to report the event in the study REDCap UAP form within 5 business days of event awareness and to the central IRB within 10 business days of event awareness.

All mentor and advisor UAPs related to study activities will be reported through the InquisitHealthTM escalation form located within the platform. The DCC will be notified by InquisitHealthTM and will have 72 business hours from this time to inform the appropriate site. It is the responsibility of the site to report it in the study REDCap UAP form within 5 business days of event awareness, and to the central IRB within 10 business days of event awareness.

•

10. STASTICIAL CONSIDERATIONS

10.1 Milestones

10.1.1 Registration Date

For all Participants:

The date the subject signs the informed consent.

10.1.2 Enrollment Date

EA-SCD Participants:

The date the baseline survey is administered to a subject (either within a healthcare setting or via survey link).

For participants on the PM arm, administration of the baseline survey and completion of the enrollment CRF occurs after confirmation of mentor matching from the DCC (see study calendar 6.3).

Mentor and Advisor Participants:

The date the participant completes all training activities. For mentors, this is the date the participant completes practice call 2. For advisors, this is the date the participant completes Peer Mentor University training.

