3.2 EA-SCD Eligibility

3.2.1 Inclusion Criteria

Subject must meet all the following applicable inclusion criteria to participate in this study:

Version 6: 12/22/2022

1. Informed consent signed by subject or parent/ guardian (where applicable) and HIPAA authorization for release of personal health information. NOTE: HIPAA authorization may be included in the informed consent or obtained separately.

- 2. Assent will be obtained in appropriately aged subjects per IRB or institutional guidelines.
- 3. Age ≥ 16 and ≤ 25 years at the time of consent AND being cared for in a PEDIATRIC SICKLE CELL PROGRAM
- 4. Any sickle cell genotype
- 5. Not known to be currently pregnant
- 6. Readily available access to a computer with internet and phone
- 7. Ability to read and understand the English language
- 8. Subject is planned to be transferred to an adult sickle cell program within 6 -12 months of consent. If an EASCD subject, at a peer mentor site, is reconsented due to a delay in matching the EASCD subject must continue to meet eligibility from the date of reconsent.

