4.2 Randomization Method and Stratification Factors

Sites will be randomized in a 1:1 fashion to either the STE+PM arm or the STE arm. To avoid cross- contamination, the randomization will be constrained so that the Novant and Atrium Health (formerly known as Carolinas Healthcare System) sites will be randomized to the same treatment arm. Prior to study activation, the LCI Department of Cancer Biostatistics will perform randomization. A stratified block randomization will be utilized, stratifying on site size (large [≥ 40 subjects] versus small [< 40 subjects]) to reduce confounding of comparisons between the treatment arms. Sites must have subcontracts executed and subjects must be registered and consented prior to starting study intervention. The study intervention is not blinded to the subject or the investigator.

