6.3 EA-SCD Participant Level Assessment Calendar

EA-SCD Participant Level Assessment Calendar																								
Study Month	Screening																							
	All Sites	Peer Mentor Sites Only	Baseline	3	6	9	12	15	18	21	24	27	30	33	36	39	42	45	48	51	54	57	60	Off Study
Eligibility Screening	•																							
Informed Consent / Assent	•																							
Demographics/Disease Characteristics ^a	•																							•
Mentor Matching ^b		● ^g																						
Acute and Ambulatory Care Visit Data Collection ^c			•	•	•	•	•	•	•	•	•	•	•	•	•	•	•	•	•	•	•	•	•	•
Transition Education Intervention Q3			• h	•	•	•	•	•	•	•	•	•	•	•	•	•	•	•	•	•	•	•	•	•
PedsQL-SCD Module			● h		•		•		•		•		•		•		•		•		•		•	•
MOS-SSS			● h		•		•		•		•		•		•		•		•		•		•	•
TIP-RFT			• h		•		•		•		•		•		•		•		•		•		•	•
ASCQ-ME QOC			• h		•		•		•		•		•		•		•		•		•		•	•
Health Care Transition Feedback Survey for Youth/Young			• h				•				•				•				•				•	•
ST3P-Up App	Downloade		Download	•	•	•	•	•	•	•	•	•	•	•	•	•	•	•	•	•	•	•	•	•

- a Demographic information collected at baseline will be re-assessed at end of study for updates and/or changes
- b During screening, EA-SCD subjects are required to provide their day/time availability for peer mentoring calls to facilitate mentor matching. These subjects MUST be matched to a mentor prior to administering baseline surveys
- c Ambulatory and acute care visits will be collected for the preceding 12 months (a month is defined, numerically, as 30.4375 days, and visit windows are based on the date of enrollment). Ambulatory visits will include visits within the healthcare setting, primary care visits, and virtual visits via telephone ONLY. Acute care visits may include, but are not limited to ED, urgent care, day hospitals, infusion centers, and hospital admissions.
- d Study visits will occur with a +/- 4 weeks window for q3mo visits. EA-SCD subject must be seen by their SCD provider during these visits. However, these visits may occur in other locations within the healthcare setting where SCD care is provided or virtually as long as required structured and targeted transition education is provided

Version 6: 12/22/2022

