e - ST3P-UP App contains "Who, What, Where, When" Sickle Cell Transition Education Modules that are required for 3-month visits. If app is not available, the education modules are provided to the sites in the QI Change Package and via PowerPoint from the DCC. Alternatively, sites can utilize any standard SCD education module.

- f Patients are encouraged but not required to download the ST3P-UP App. Directions to access the ST3P-UP app and instructions for use will be provided to participants by local site Transition Coordinators. Transition Coordinators are encouraged to use study- provided tablets and/or iPads to facilitate follow-up visit adherence communication and for structured transition education.
- g For PM sites, mentee availability should be captured in the REDCap database at the time of consent. For subjects with delayed enrollment, confirmation of availability should be revisited at the time of Mentor-Mentee matching.
- h Every effort should be made to complete the baseline survey within a healthcare setting but if administration occurs via survey link, this must be provided to the participant within 72 hours from the date of consent (for the STE arm) or from the date of match (for the PM arm). The survey link will expire within 2 weeks of receipt. If the survey remains incomplete after two weeks, please discontinue efforts to contact the participant for completion of the baseline survey.

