10.4 Analysis Populations

All EA-SCD participant-level analyses will be conducted on the population of all enrolled EA-SCD participants (consented EA-SCD participants who are enrolled per section 10.1.2), regardless of how long the EA-SCD participant was on study or regardless of the extent of data missingness.

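### On the PM arm alone, enrolment waits for a mentor match and only the enrolled are analysed; report who is lost before enrolment and pre-specify a tipping-point analysis

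*Combined protocol and SAP*

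**What the plan says.** Allocation comes first. Section 4.2: "Prior to study activation, the LCI Department of Cancer Biostatistics will perform randomization". Consent follows in both arms, and section 10.1.2 defines enrolment as the date the baseline survey is administered.

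The arms then part. For PM sites, section 10.1.2 adds: "For participants on the PM arm, administration of the baseline survey and completion of the enrollment CRF occurs after confirmation of mentor matching". Note b to the calendar in 6.3 is firm on this: "These subjects MUST be matched to a mentor prior to administering baseline surveys". Under note h, when the baseline survey goes out by link, the 72-hour clock runs "from the date of consent (for the STE arm) or from the date of match (for the PM arm". No limit is stated on how long a participant may wait for a match; the 90-day rule in 5.2.3 covers mentors and advisors only.

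The plan expects delay. Note g says "For subjects with delayed enrollment, confirmation of availability should be revisited at the time of Mentor-Mentee matching". Section 3.2.1 provides that a participant at a PM site who "is reconsented due to a delay in matching the EASCD subject must continue to meet eligibility from the date of reconsent".

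Anyone who leaves between consent and enrolment is a screen failure (3.6). Section 10.4 bases every participant-level analysis on those enrolled: "consented EA-SCD participants who are enrolled per section 10.1.2".

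Several planned items come near the point. The flow diagram covers everyone consented, with reasons for withdrawal (10.5.2). Time from first consent to enrolment on PM is an endpoint (10.3.3), summarised descriptively (10.5.5). The primary model adjusts for baseline acute care visits, and two analyses address differential accrual over time (10.5.4).

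**The concern.** Randomisation protects a comparison of the people the sites would have contributed under either allocation. Here PM participants must pass a step that STE participants never face, and those who fail it leave the analysis. Matching depends on the age gap, call availability and the mentee's gender preference (5.2.3), and on mentor capacity. PM sites alone also repeat the eligibility check when matching delay leads to re-consent.

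If those lost while waiting would have had more acute care visits than those matched, the enrolled PM group looks better than it should; if fewer, worse. The design effect is a 20% reduction (10.2), so selection could imitate or hide a material part of it.

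None of the planned items bounds this. The flow diagram and waiting times are descriptive. The year-of-enrolment term and the contemporaneous subset both stay within the enrolled. The missing-data methods (10.5.6) concern covariates and PROs. Visit history is a baseline item for enrolled participants (6.4.2), and 7.1 asks for no end-of-study form from those who withdraw before enrolment.

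**Working it through.** **Yardstick.** The plan has no figure for pre-enrolment loss. Its design effect is 6 to 4.8 visits a year, and its sample size reproduces: (1.960+1.036)² × (6+4.8)/1.2² = 67.3 per arm under individual randomisation (plan: 67). With 7 sites per arm, ICC 0.05 and CV 0.60, 67 × 0.95/(7 - 67 × 1.36 × 0.05) = 26.04 per site, or 182.3 per arm (plan: 183).

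**Unadjusted shift.** Let u be the share of PM consents never enrolled and y their visit rate relative to the enrolled. With no true effect and no STE loss, the PM rate shifts by 1/(1 - u + u·y) - 1. Neither u nor y is documented. I assume u = 10%, 20%, 30% and y = 0.5 or 2, symmetric on the ratio scale.

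| PM loss u | y = 0.5 | y = 1 | y = 2 |
|---|---|---|---|
| 10% | 1/0.95: +5.3% | 0 | 1/1.1: -9.1% |
| 20% | 1/0.90: +11.1% | 0 | 1/1.2: -16.7% |
| 30% | 1/0.85: +17.6% | 0 | 1/1.3: -23.1% |

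**After baseline adjustment, stable personal rates.** Simulation settings: 300 consented per arm; no true effect; no STE loss; gamma-distributed personal rates with mean 4.5 a year (assumed, between the 4.2 and 5.3 in section 1.1) and dispersion (6.8² - 4.2)/4.2² = 2.38; loss depending on the personal rate; 12-month baseline and 24-month outcome; Poisson log-link model without site effects. Across the grid above, the residual shift runs from about +8% to -10% with raw baseline visits, and from about +2% to -2.5% with log(1+visits). Section 10.5.4 does not state the scale.

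**After baseline adjustment, changing rates.** Suppose 40% of participants take a new rate at transition and loss tracks the later rate. With u = 20% and y = 2, the residual shift is -13.9% (raw) or -12.8% (log), against -16.7% unadjusted. Neither scale helps much.

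**Tipping point.** RR among all consented = RR among enrolled × (1 - u_PM + u_PM·y_PM)/(1 - u_STE + u_STE·y_STE). Setting this to 1 with no STE loss gives y_PM = 1 + (1/RR - 1)/u_PM.

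- Estimated 20% reduction (1/0.8 - 1 = 0.25): y_PM = 3.5, 2.25 or 1.83 at 10%, 20% or 30% PM loss.
- Estimated 10% reduction (1/0.9 - 1 = 0.111): y_PM = 2.11, 1.56 or 1.37.
- Estimated 20% reduction with 10% STE loss at the same relative rate y: at 20% PM loss, 0.8(0.8 + 0.2y) = 0.9 + 0.1y gives y = 4.33; at 30%, y = 2.43; at 10% the losses cancel and there is no tipping point.

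Applied to an adjusted RR, y is the relative rate not explained by baseline visits.

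**The case against.** **The comparison may no longer be central.** The Synopsis says the PM comparator cannot be assessed quantitatively in the way first intended, and adds qualitative work. That lowers the stakes. But 10.5.4 still specifies the arm comparison, so the point stands.

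**No loss is documented.** This stands in full: every percentage above rests on assumed u and y. A reader might infer that the PM result is biased towards benefit, since the five-year age gap, with mentors aged 26 or older, can bind only at ages 22 to 25, within the highest-use age band in section 1.1. The documents do not support that. At those ages the rule excludes only mentors aged 26 to 29, nothing shows that older mentors are scarce, and the other matching factors have no documented link to visit rate.

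**Much is already planned.** A reader might infer that nobody could judge the selection from the planned reports. That goes too far: if the flow diagram gives consented and enrolled counts by arm, the one-line formula can be applied to it. Still, 10.5.2 does not ask for the characteristics or waiting times of those lost, and nothing commits the sponsor to the calculation.

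**A waiting limit.** A reader might infer from "Subject is planned to be transferred to an adult sickle cell program within 6 -12 months of consent" and the re-consent check that a participant can wait at most 0 to 6 months (6 - 6 and 12 - 6). That needs re-consent to occur and the planned transfer date to stay unchanged. The protocol says neither.

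**The covariate scale is a separate modelling choice.** Partly so. In the cells checked, the log scale left no more bias than raw counts beyond simulation error, and it was more precise. Its large gain appears only when personal rates are stable. The simulations also omit site effects, use a mean of 4.5 rather than the design's 6, and assume no STE loss.

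**Conclusion.** The concern holds as a conditional one. The analysis set depends on a post-allocation event in the PM arm only, and no planned analysis bounds the effect. There is bias only if those lost before a match differ in visit rate from those matched. Size and direction are unknown.

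Under the assumed range, the unadjusted shift reaches +17.6% or -23.1% at 30% loss, and +5.3% or -9.1% at 10%. How far baseline adjustment reduces this depends on how well past visits predict later ones. At 10% loss, only a large difference in rate (3.5 times) would erase an estimated 20% reduction; at 30% loss, 1.83 times would. The documents do not support a claim that the trial's result is biased. They support asking the plan to show how sensitive it is. The change should be made before the final analysis.

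**What to change.** Keep the enrolled-set primary analysis and add the following.

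- **10.4:** state that the population excludes consented participants lost before enrolment, including those lost while awaiting a match on PM.
- **10.5.2:** report consented-not-enrolled participants by arm, with reasons, screening characteristics and time from first consent. Count failures of the re-consent eligibility check as losses.
- **10.5.4, tipping point:** at the observed by-arm shares lost, give the relative visit rate among those lost that would remove the estimated effect. Show it with STE losses at the enrolled rate and at the same relative rate as PM.
- **10.5.4, covariate:** enter baseline visits as log(1+visits), with the raw scale as a sensitivity analysis, and note that this helps only as far as past visits predict later ones.

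The cost is wording, one change to a covariate, and a little more analysis and reporting. Consent dates (10.1.1), screen failures (3.6) and screening characteristics (6.4.1) are already collected. Reasons for loss may have to come from the research chart, given 7.1. The tipping point needs no outcome data on those lost; for the same reason, it shows sensitivity to the selection without removing it.
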